Administrative Letter 04	02-Aug-2018	Clarified participation in the actigraphy and Holter monitoring sub-studies is optional for sites and patients. Furthermore, minor revisions are made to the PK Sampling schedule to reflect the required samples for Part II. In addition, a note is added to the 12-lead ECG procedure at hour 24 to clarify that it is only applicable to sites in Germany. Additional minor administrative corrections are also added.
Administrative Letter 03	27-Apr-2018	Corrected a typographical error in the “summary of key changes for revised protocol 02” table, which incorrectly noted the actigraphy and holter monitor sub-studies as exploratory endpoints. The actigraphy and holter monitor sub-studies are exploratory objectives.
Revised Protocol 02	09-Apr-2018	Expansion of screening period, addition of Holter Monitoring in a subset of patients, addition of Actigraphy monitoring in a subset of patients, and clarifications throughout the document.
Administrative Letter 02	05-Dec-2017	Clarifies secondary packaging of BMS986-231 as a carton containing 5 or 6 vials.
Administrative Letter 01	14-Feb-2017	Administrative clarifications throughout the protocol.
Revised Protocol 01	11-Oct-2016	Incorporates changes from Amendment 01.
Amendment 01	11-Oct-2016	Addition of two unblinded interim analysis, addition of Sensory Motor Survey, clarification and updates to Eligibility criteria, and additional edits throughout the document to improve readability.
Original Protocol	28-Jun-2016	Not applicable

[figure not shown]
OVERALL RATIONALE FOR REVISED PROTOCOL 02C:

The purpose of this amendment to advise that subjects in Japan who were enrolled after the end of global Part II enrollment will be followed for safety and rehospitalization endpoints through Day 32 only. The global study provides adequate safety follow up data and additional Day 182 data from the Japanese population is not necessary. A final analysis will be performed following completion of the last visit (Day 32) of the last enrolled Japanese subject to complete an analysis of the Japanese patient data. This revision applies to all subjects enrolled in Japan, excluding the subjects enrolled as part of the 210 subject global cohort (Part II, Cohort 2).

SUMMARY OF KEY CHANGES FOR REVISED PROTOCOL 02C		
Section Number & Title	Description of Change	Brief Rationale

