Central Laboratory Assessments			See Section 5.3.5.2 for Analytes
Hematology and Serum Chemistry		X	
Hs Troponin T		X	
NT-proBNP, Serum Cystatin C, NGAL		X	
CRP		X	
Urinalysis		X	
Urine creatinine, Na+, and K+		X	
Efficacy Assessments			
Resting Dyspnea measured by the Numerical Rating Scale (NRS) ^a		X	
Other Assessments			
Sensory Motor Survey		X	

^a If subject is receiving supplemental oxygen, perform NRS without removing oxygen

Table 5.1-2: Treatment and In-Hospital Follow-up (CV013011)

Procedure	Hour 0-23 ^a (Post Rand, Day 1)	Hour 24 ± 2	Hour 48 ± 2	Hour 72 ± 2	Hour 96 ± 2	Hour 120 ± 2 or Discharge ^{b c}	Notes (Time is relative to start of dosing)
Randomize Subject	X						Randomization must take place before Hour 0
Administer Study Medication		X					48 hour continuous infusion *Study medication infusion begin promptly after randomization*
Safety Assessments							
Body Weight		X	X	X	X	X	
Vital Signs: Blood Pressure and Heart Rate ^d	X	X	X	X	X	X	Perform Semi-Recumbent (at a 30° angle) Day 1: Hours 0, 0.25 (15 min), 0.5 (30 min), 0.75 (45 min), 1, 1.5, 2, 4, 5* , 6, 8, 9* , 10, 12, 14, 16, 18, 20, 22 Hours: 24, 28, 32, 36, 40, 44 Hours 48, 54, 60, 66 Hour 72 Hour 96 Hour 120 Perform measurements before IV bag change, when possible. Repeats as per Section 5.3.1 Perform also if signs or symptoms of hypotension *Part I (Cohort 1) only
Respiratory Rate	X	X	X	X	X	X	Day 1: Hours 6 and 12
Use of Oxygen Supplementation,	X	X	X	X	X	X	Day 1: Hours 6 and 12

Table 5.1-2: Treatment and In-Hospital Follow-up (CV013011)

Procedure	Hour 0-23 ^a (Post Rand, Day 1)	Hour 24 ± 2	Hour 48 ± 2	Hour 72 ± 2	Hour 96 ± 2	Hour 120 ± 2 or Discharge ^{b c}	Notes (Time is relative to start of dosing)
Oxygen Saturation							
Temperature		X	X	X	X	X	
12-Lead ECG		X	X	X		X	
Telemetry Monitoring	X						Continuous monitoring through Hour 50

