7.3.2 Demographics and Baseline Characteristics

Frequency distributions and summary statistics for demographic and baseline variables will be presented by treatment group and for all subjects combined for all treated subjects. Demographic variables to be summarized include: age, gender, race, and geographic region. See Table 7.3-1 for countries in each region.

Table 7.3-1: Demographics and Baseline Characteristics

Region	Country
North America	Canada and United States
Europe	Czech Republic, France, Germany, Greece, Italy, Netherlands, Poland, Spain, and United Kingdom
Latin America	Argentina

Baseline variables to be summarized include the following:

- Physical measurements (height, body weight, body mass index)
- Vital signs (systolic blood pressure, diastolic blood pressure, and heart rate)
- Disease characteristics
 - New York Heart Association Class prior to admission
 - Ejection fraction (%)
 - Heart failure etiology (as collected in the CRF Heart Failure Etiology page at screening)
 - Number of heart failure hospitalizations in past year
 - Time since original HF diagnosis to first treatment of study drug
 - Time since first diuretic use in the current episode of decompensation to first treatment of study drug
 - Comorbidities listed in “Specific Disease History” CRF page, including but not limited to coronary artery disease, hypertension, diabetes, and presence of atrial fibrillation
- Important laboratory variables (including NT-proBNP, serum sodium and eGFR)
- Current heart failure medications

Start time of first diuretic use will be obtained from “Previous and Concomitant Intravenous Medications” CRF page.

Current heart failure medications will be taken from CRF previous and concomitant IV and non-IV medications pages with Use of “Heart Failure” and start date prior to first treatment of study drug. The CRF pages collect IV medications administered starting from one week prior to randomization.

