8.3 Hour Ranges for Analysis of Time Points

Subjects do not always adhere strictly to the visit schedule timing in the protocol. The hour ranges for the analyses of dyspnea measured by 11-point NRS and 7-point Likert scale and patient global assessment (PGA) measured by 7-point Likert scale are defined in Table 8.3-1. The hour ranges for the analyses of laboratory ECG are defined in Table 8.3-2 and 8.3-3, respectively. The hour ranges for the analyses of assessments measured at Hour 24, 48, 72, 96, and 120 (including respiratory rate and temperature) are defined in Table 8.3.4.

Table 8.3-1: Hour Ranges for Analyses of Dyspnea Measured by 11-point NRS and 7-point Likert Scale and PGA Measured by 7-point Likert Scale

Nominal Visit	Target Hour	Hour Ranges
Baseline	Pre-dose	Randomization to \leq Hour 0
Hour 6	Start of infusion + 6	\geq Hour 3 to < Hour 9
Hour 12	Start of infusion + 12	\geq Hour 9 to < Hour 18
Hour 24	Start of infusion + 24	\geq Hour 18 to < Hour 36
Hour 48	Start of infusion + 48	\geq Hour 36 to < Hour 60
Hour 72	Start of infusion + 72	\geq Hour 60 to < Hour 96
Hour 120	Start of infusion + 120	\geq Hour 96 to \leq Hour 132

Table 8.3-2: Hour Ranges for Analyses of Laboratory Measurements

Nominal Visit	Target Hour	Hour Ranges
Baseline	Pre-dose	Randomization to \leq Hour 0
Hour 24	Start of infusion + 24	\geq Hour 12 to < Hour 36
Hour 48	Start of infusion + 48	\geq Hour 36 to < Hour 60
Hour 72	Start of infusion + 72	\geq Hour 60 to < Hour 96
Hour 120	Start of infusion + 120	\geq Hour 96 to \leq Hour 132

Table 8.3-3: Hour Ranges for Analyses of ECG

Nominal Visit	Target Hour	Hour Ranges
Baseline	Pre-dose	Randomization to \leq Hour 0
Hour 48	Start of infusion + 48	\geq Hour 24 to < Hour 60
Hour 72	Start of infusion + 72	\geq Hour 60 to < Hour 96
Hour 120	Start of infusion + 120	\geq Hour 96 to \leq Hour 132

Table 8.3-4: Hour Ranges for Analyses of Respiratory Rate and Temperature

Nominal Visit	Target Hour	Hour Ranges
Baseline	Pre-dose	Randomization to \leq Hour 0
Hour 24	Start of infusion + 24	\geq Hour 12 to < Hour 36
Hour 48	Start of infusion + 48	\geq Hour 36 to < Hour 60
Hour 72	Start of infusion + 72	\geq Hour 60 to < Hour 84
Hour 96	Start of infusion + 96	\geq Hour 84 to < Hour 108
Hour 120	Start of infusion + 120	\geq Hour 108 to \leq Hour 132

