Vital signs (blood pressure and heart rate) are assessed at Hours 0, 0.5, 1, 2, 4, 5 (for Part I only), 6, 8, 9 (for Part I only), 10, 12, 14, 16, 18, 20, 22, 24, 28, 32, 36, 40, 44, 48, 54, 60, 66, 72, 96, 120, and Day 32. The hour ranges for the analyses of vital signs are defined in the same manner as in Table 8.3-1 to Table 8.3-4. The hour ranges around planned measurement times are based on the midpoint between planned measurement times, for example, Hour Ranges for Hour 24 is \geq Hour 23 to < Hour 26. Hour Ranges for Hour 120 are \geq Hour 108 to \leq Hour 132. The value collected at the Day 32 visit will be used for the Day 32 time regardless of time ranges.

The hour ranges for the analyses of oxygen saturation are defined in the same manner as in Table 8.3-1 for Baseline, Hours 6, 12, 24, 48, and Table 8.3-4 for Hours 72, 96, and 120.

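### The SAP 8.3 windows for respiratory rate and ECG do not match the current protocol schedule, so some scheduled values leave the by-time-point safety summaries or, if no nearer record exists, appear under the wrong hour

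*SAP*

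**What the plan says.** **Respiratory rate.** In Protocol Table 5.1-2 the note on this row reads "Day 1: Hours 6 and 12", and the row is then marked at Hours 24, 48, 72, 96 and 120 or discharge. SAP 8.3 instead counts it among the "assessments measured at Hour 24, 48, 72, 96, and 120 (including respiratory rate and temperature") and assigns it to the table titled "Table 8.3-4: Hour Ranges for Analyses of Respiratory Rate and Temperature". After baseline, that table begins with Hour 24, defined as ≥ Hour 12 to < Hour 36.

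**Oxygen saturation.** The protocol gives it the same Day 1 hours as respiratory rate. The SAP treats it differently: the "analyses of oxygen saturation are defined in the same manner as in Table 8.3-1 for Baseline, Hours 6, 12, 24, 48", with Table 8.3-4 used for Hours 72, 96 and 120.

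**ECG.** Protocol Table 5.1-2 marks the 12-lead ECG at Hours 24, 48, 72 (each ± 2) and 120 or discharge. SAP Table 8.3-3 has rows for Baseline, Hour 48, Hour 72 and Hour 120 only. The Hour 48 row is "Hour 24 to < Hour 60", lower limit included.

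**Scope of the Hour 24 ECG.** In the protocol's Document History, the entry for Administrative Letter 04 (02-Aug-2018) says that "a note is added to the 12-lead ECG procedure at hour 24 to clarify that it is only applicable to sites in Germany". The ECG row of the later Revised Protocol 02c table shows no such note.

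**Other rules that bear on this.** SAP 2.4 bases the SAP on Revised Protocol 01. SAP 8.4 resolves several records in one window in favour of the one closest to the planned time. SAP 7.6.2.5 lists every recorded ECG, lists subjects with out-of-range intervals separately, and tabulates ECG parameters by time point and treatment.

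**The concern.** An analysis window decides whether a measurement appears in a by-visit table and under which label. If a scheduled visit has no row, its values either fall in a gap or enter a neighbouring visit's window. Both can happen here.

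For respiratory rate, the first 12 hours of the infusion would not be summarised. For ECG, values taken half-way through the planned 48-hour infusion could be absent from the summary, or could stand in as Hour 48 for a subject with no ECG near Hour 48. The Hour 48 window is 60 − 24 = 36 hours wide: 24 hours before the planned end of infusion and 12 hours after it. A value labelled Hour 48 can therefore come from a very different point of exposure. In a trial whose purpose is safety and tolerability of the infusion, the by-time-point safety tables should show what was measured, and when.

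**Working it through.** **Inputs.** Planned hours come from Protocol Table 5.1-2 and printed windows from SAP Tables 8.3-1 to 8.3-4. SAP 8.3 states its construction rule for blood pressure and heart rate: "The hour ranges around planned measurement times are based on the midpoint between planned measurement times". The upper limit of Hour 132 for the last visit is taken as printed.

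**Formula.** For planned hours t₁ < t₂ < …, the window for tᵢ runs from (tᵢ₋₁ + tᵢ)/2 to (tᵢ + tᵢ₊₁)/2.

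**Step 1: reproduce the printed tables.**

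- ECG with visits 0, 48, 72, 120: (0+48)/2 = 24, (48+72)/2 = 60, (72+120)/2 = 96. Windows: Hour 48 = 24–60, Hour 72 = 60–96, Hour 120 = 96–132. This is Table 8.3-3 exactly.
- Respiratory rate with visits 0, 24, 48, 72, 96, 120: limits 12, 36, 60, 84, 108. Windows: Hour 24 = 12–36, Hour 48 = 36–60, Hour 72 = 60–84, Hour 96 = 84–108, Hour 120 = 108–132. This is Table 8.3-4 exactly.

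So the Hour 24 lower limit for the Hour 48 ECG is not a typing error. The printed windows are what the midpoint rule gives for a schedule with no Hour 24 ECG and no Hour 6 or 12 respiratory rate.

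**Step 2: place the protocol's scheduled values in the printed windows.** The protocol states no tolerance for respiratory rate at Hours 6 and 12. The ± 0.25 h used below is borrowed from blood pressure and heart rate, for illustration only.

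| Scheduled value | Taken at | Printed SAP window |
|---|---|---|
| Respiratory rate, Hour 6 | 5.75 to 6.25 h | none |
| Respiratory rate, Hour 12 | 11.75 to < 12 h | none |
| Respiratory rate, Hour 12 | 12 to 12.25 h | Hour 24 |
| ECG, Hour 24 ± 2 | 22 to < 24 h | none |
| ECG, Hour 24 ± 2 | 24 to 26 h | Hour 48 |

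**Step 3: apply the closest-record rule.** An ECG at 24 to 26 h lies 22 to 24 h from Hour 48; an on-schedule Hour 48 ECG lies within 2 h. The earlier ECG is passed over whenever the later one exists, and is reported as Hour 48 only when no nearer ECG does. Likewise, a respiratory rate at 12 to 12.25 h is about 12 h from Hour 24 and yields to any on-schedule Hour 24 value. Omission is thus the usual outcome, and mislabelling the exception.

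**Step 4: apply the same rule to the protocol's own visits.**

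- ECG with 0, 24, 48, 72, 120: Hour 24 = 12–36, Hour 48 = 36–60, Hours 72 and 120 unchanged. The Hour 24 and 48 limits are those of laboratory Table 8.3-2.
- Respiratory rate with 0, 6, 12, 24, 48, 72, 96, 120: Hour 6 = 3–9, Hour 12 = 9–18, Hour 24 = 18–36, Hours 48 to 120 unchanged. The Hour 6, 12 and 24 limits are those of Table 8.3-1, which the SAP already applies to oxygen saturation.

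**The case against.** The strongest reply concerns the ECG. Administrative Letter 04 describes the Hour 24 ECG as German-only, and Table 8.3-3 is coherent for a schedule without it. Germany is one of nine countries in the SAP's European region ("Czech Republic, France, Germany, Greece, Italy, Netherlands, Poland, Spain, and United Kingdom"), alongside Canada, the United States and Argentina. This stands in part. The later 02c table does not carry the restriction, so the protocol itself needs reconciling. Even on the narrow reading, German Hour 24 ECGs still have no proper window.

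Second, the SAP rests on Revised Protocol 01, whose schedule is not in the documents. This also stands: one cannot say that the tables were wrong when written, only that they do not fit the current schedule.

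Third, the consequence is limited. All ECGs and all out-of-range intervals remain listed. Neither measure is a primary or secondary endpoint, and SAP 7.1 plans no significance testing. Apart from the windows, no visible SAP analysis section names respiratory rate. All of this stands and sets the size of the point.

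A reader might infer two stronger things. One is that Hour 24 ECGs are lost for whole arms, about 210/3 = 70 subjects each in Part II. The documents do not support that while Administrative Letter 04 restricts the assessment to German sites. The other is that the trial would have no mid-infusion ECG summary. Protocol 5.3.7 plans Holter recordings in 51 Part II patients under a separate analysis plan. Extractions during the infusion include Hour 14, and the synopsis describes a by-time-point QTcF analysis and outlier analyses covering PR, QRS and QTcF.

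**Conclusion.** The mismatch is real and its effect is modest.

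- **Respiratory rate** is the firmer half. It applies at all sites and in both parts, and two of the first three scheduled times after the start of infusion (Hours 6, 12 and 24) have no row. The SAP is also inconsistent with itself, since oxygen saturation has the same Day 1 schedule and does get those rows.
- **ECG** is the narrower half. Hour 24 safety ECGs are left out of the by-time-point summary, or labelled Hour 48 when no nearer ECG exists. The number affected cannot be given: the documents do not report how many subjects are at German sites, or how ECG times spread across the ± 2 h tolerance.

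The damage is confined to descriptive safety summaries. The primary hypotension analysis, the secondary endpoints, the ECG listings and the Holter analysis are untouched. The conclusion assumes that the printed windows will be programmed as they stand against data collected under the current schedule. The windows should be corrected before programming, because as written they are wrong rules for that schedule rather than missing detail.

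**What to change.** **Respiratory rate.** Use the windows SAP 8.3 gives oxygen saturation: Table 8.3-1 limits for Hours 6 (≥ 3 to < 9), 12 (≥ 9 to < 18), 24 (≥ 18 to < 36) and 48 (≥ 36 to < 60), and Table 8.3-4 from Hour 72. Correct the sentence that treats it as measured only from Hour 24.

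**ECG.** First reconcile the protocol table with Administrative Letter 04 on which sites perform the Hour 24 ECG. Then, in Table 8.3-3, set Hour 48 to ≥ Hour 36 to < Hour 60 and add Hour 24 as ≥ Hour 12 to < Hour 36, both already the limits in Table 8.3-2. Label the Hour 24 row with the sites it covers.

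If the sponsor prefers to list the extra values only, the SAP should say so, and the Hour 48 ECG window should still open at Hour 36.

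**Cost.** Two table edits and a sentence or two of text, with no new data. There is one small downside: if the Hour 24 ECG is German-only, that row describes a small subset and, without its label, could be mistaken for a study-wide time point.

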8.4 Multiple Measurements

For longitudinal summaries of data, if there are multiple records within the same Hour ranges, then the value closest to the time of the planned time points is selected unless specified otherwise.

Laboratory Measurements

For tabulations of changes from baseline or shift analyses, if multiple laboratory measurements are obtained within the same nominal visit, then the measurement obtained on the day closest to the target day for that nominal visit will be used; in the case of a tie, the measurement obtained on the earlier day will be used in the analyses.

For tabulations of incidence of marked abnormalities (e.g. ALT > 3xULN), if multiple laboratory measurements are obtained within the same nominal visit, then the worst measurement within the nominal visit window nominal visit will be used.

Vital Signs and ECGs

If multiple vital sign or ECG measurements are obtained within the same nominal visit, then the measurement obtained on the day closest to the target day for that nominal visit will be used; in the case of a tie, the measurement obtained on the earlier day will be used in the analyses.

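### SAP 8.4 chooses among repeated laboratory, vital-sign and ECG values by day although SAP 8.3 sets targets and windows in hours, so same-day readings tie without a tie-break and day-spanning readings can resolve to the farther one

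*SAP*

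**What the plan says.** SAP 8.4 begins with a general rule for several records in one window: "then the value closest to the time of the planned time points is selected unless specified otherwise". Two later paragraphs specify otherwise.

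- Laboratory values, for change-from-baseline tables and shift analyses: "then the measurement obtained on the day closest to the target day for that nominal visit will be used". For two readings equally near by that measure, the paragraph adds this: "in the case of a tie, the measurement obtained on the earlier day will be used in the analyses".
- Vital signs and ECGs, with no restriction on the type of table: "If multiple vital sign or ECG measurements are obtained within the same nominal visit", the same nearest-day choice and the same tie rule apply.

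Marked laboratory abnormalities have a separate rule: "then the worst measurement within the nominal visit window nominal visit will be used".

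SAP 8.3 works in hours. For vital signs, "The hour ranges around planned measurement times are based on the midpoint between planned measurement times". The tables headed "Hour Ranges for Analyses of Laboratory Measurements" and "Hour Ranges for Analyses of ECG" give target hours and hour ranges. No target day is defined for any in-hospital visit.

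**The concern.** A nearest-day rule suits visits that are days or weeks apart. Here most vital-sign windows last a few hours, and the laboratory and ECG windows last 24 to 36 hours. Within one day the rule has nothing to compare, and the earlier-day tie rule cannot separate two readings with the same date. Across midnight the rule compares dates instead of distances.

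Repeat readings are part of this protocol. Section 4.5.1 requires a second SBP within 15 minutes after a value below 95 mm Hg without symptoms. Table 5.3.1-1 adds readings at 0.5, 1, 2, 4 and 6 hours after a dose modification (to 4 hours for an interruption). The vital-sign summaries in SAP 7.6.2.6 therefore depend on an unstated choice among the low value, its repeat and the recovery value. That choice arises mostly in subjects whose blood pressure has fallen.

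**Working it through.** **1. The plan's own windows.** Each vital-sign window runs between the midpoints to the neighbouring planned hours.
- Hour 24: (22 + 24)/2 = 23 to (24 + 28)/2 = 26, as the SAP states.
- Hour 120: lower limit (96 + 120)/2 = 108, as the SAP states; the upper limit of 132 is given.
- Widths: 0.5 to 5 h through Hour 48. Hours 54, 60 and 66 are 6 h each (51–57, 57–63, 63–69). Hour 72 is 69–84, or 15 h. Hours 96 and 120 are 24 h each.
- Laboratory windows: 24 h at Hours 24 and 48; 36 h at Hours 72 and 120. ECG windows: 36 h each.

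**2. How often the rule gives no answer.** Assumptions: infusion start uniform over the clock, two readings uniform within a window of width w hours, day read as calendar day. The expected gap between the readings is w/3, so for w ≤ 24 the chance that midnight separates them is (w/3)/24 = w/72. The same-day share is 1 − w/72.
- Vital signs Hour 24: 1 − 3/72 = 95.8%.
- Vital signs Hour 48: 1 − 5/72 = 93.1%.
- Vital signs Hours 54 to 66: 1 − 6/72 = 91.7%.
- Mean width through Hour 48 (20 windows, without the Part I-only Hours 5 and 9): 50.75/20 = 2.54 h, giving 96.5%.
- Laboratory Hours 24 and 48: 1 − 24/72 = 66.7%.
- 36-hour laboratory and ECG windows: about 52%, by simulation.

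A simulation of 400,000 pairs per window agrees (95.8% at Hour 24, 93.0% at Hour 48, 67% for laboratory Hours 24 and 48).

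**3. A same-day laboratory tie.** Infusion starts at 02:00 on Day 1. The Hour 72 draw is at 02:00 on Day 4. A discharge draw at Hour 86 is at 16:00 on Day 4. The two are 14 h apart, so the protocol's 12-hour exemption from repeating discharge assessments does not apply. Both fall in the Hour 72 window (60 to < 96) on the same date. One is 0 h from target and the other 14 h, yet the rule does not choose. NT-proBNP and troponin T are drawn at both visits.

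**4. A wrong choice with on-schedule ECGs.** Protocol Table 5.1-2 marks ECGs at Hour 24 ± 2 and Hour 48 ± 2; the document history (Administrative Letter 04) limits the Hour 24 ECG to Germany, which is in the SAP country list. The SAP's Hour 48 ECG window is Hour 24 to < 60, so it can hold both. Infusion starts at 23:00 on Day 1.
- Target Hour 48: Day 3, 23:00.
- ECG at Hour 25.5: Day 3, 00:30; distance 48 − 25.5 = 22.5 h.
- ECG at Hour 49.5: Day 4, 00:30; distance 49.5 − 48 = 1.5 h.

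The first ECG is on the target day, so it is chosen, although it is 21 h farther from target.

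**5. How often the farther reading wins.** In the same simulation, among pairs that span two days, the rule picks the farther reading in about 9% (vital signs Hour 72) to 25% (laboratory Hour 24), and in 19% for vital signs Hour 24 and ECG Hour 48. As a share of all pairs this is 0.8% for vital signs Hour 24, 8.4% for laboratory Hour 24 and 9.2% for ECG Hour 48.

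**6. Reading day as 24 hours from infusion start.** This does not rescue the rule. Vital-sign windows containing no multiple of 24 h then tie in 100% of pairs. At Hour 24 the farther reading is picked in about 33% of all pairs. For example, Hour 25.5 (1.5 h away, same 24-hour block as Hour 24) beats an on-schedule Hour 23.75 (0.25 h away, previous block). The ECG example in step 4 does resolve correctly under this reading, so that example rests on calendar days.

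**The case against.** The strongest reply is that the default still operates underneath the specific rule. On this view the nearest-day rule settles only the day, and where all candidates share a day nothing else has been specified, so closest in time decides. A sensible programmer might do this. The SAP does not say so, however, and the fallback would leave choices across midnight unchanged.

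A second reply is that wrong choices are uncommon. This is partly right: for Hour 24 vital signs the simulated share is under 1% of pairs. Central laboratory draws are scheduled once per visit, and extra laboratory values arise mainly from an early discharge visit.

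A third reply concerns reach, and it stands. Because repeats cluster in subjects with low SBP, a reader might infer that the hypotension results are at risk. The documents do not support that. SAP 8.1 gives the primary endpoint and confirmed SBP < 90 their own 30-minute confirmation rule, identifies symptomatic hypotension from CRF symptoms, and counts down-titrations, interruptions and discontinuations from CRF reasons. None of these passes through SAP 8.4. The dyspnea scales keep the closest-in-time default, and no significance testing is pre-specified.

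**Conclusion.** The nearest-day rule is wrong as written for hour-based windows. It gives no answer for readings on the same day, which is the usual case in vital-sign windows through Hour 66, and it can select the farther reading when two days are involved. It would be too strong to say that it always picks the farther one across midnight; under the stated assumptions it does so in roughly 9% to 25% of day-spanning pairs, depending on the window.

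The effect is confined to descriptive by-time-point summaries of vital signs, ECG parameters and laboratory change from baseline. These include NT-proBNP, a secondary endpoint, and troponin T. SAP 7.11 names renal function among the inputs to the dose decision; any such table built on laboratory change from baseline would use this rule, but the documents do not say how renal function will be shown.

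The percentages rest on uniform start times and uniform readings. They show how the rule behaves and do not predict how many subjects will be affected. The documents give no basis for estimating the effect on a mean SBP or a laboratory mean.

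**What to change.** In the laboratory change/shift paragraph and in the vital-sign/ECG paragraph of SAP 8.4, replace the nearest-day criterion with elapsed time from infusion start closest to the target hour, and send exact ties to the earlier time instead of the earlier day. This restores the section's own default. The worst-value rule for marked abnormalities stays as it is. The cost is a wording change in the SAP and the matching programming specification; no data collection, endpoint or sample size changes.
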